1.2 Study Rationale

The central question of this study is whether a biomarker-signature -supported antibiotic treatment decision matrix can have a beneficial impact on antibiotic use and patient outcomes in an ICU population.

We propose to combine the evaluation of this test pragmatically with an antibiotic treatment decision matrix in a manner that mimics real-life but is as close as possible to a “best-case” scenario - modeling our study on a successful NIH-funded multicenter trial of PCT-guided use of antibiotics which avoided many of the biases that previously led to overestimating the benefit of PCT⁴². This study will inform researchers, practitioners, and health-care administrators whether and how this recently commercialized diagnostic assay should be incorporated in routine practice, ensuring diagnostic stewardship considerations are integrated within AMS considerations.

1.3 Potential impact

We anticipate this study will demonstrate that an evidence-based implementation strategy of a BV-supported antibiotic treatment decision matrix can lead to a significant reduction of antibiotic use without compromising patient safety in an ICU population. If antibiotic exposure is not reduced in the intervention group (non-superior), we would not recommend implementation of the BV test widely. We would evaluate if the finding can be attributed to an unexpectedly lower antibiotic use in the control arm (compared to usual practice in ICU) and would recommend hospitals choose either the BV test or clinical assessment of prescription quality to reduce antibiotic use in ICU. If our findings demonstrate reduction in antibiotic use but evidence of harm in the intervention group, we will not recommend widespread implementation of the BV test but would carefully analyze our adverse outcome results to determine if select events are driving the overall finding. We would further perform subgroup analyses to assess if these outcomes occurred predominantly in specific groups.

2. MEDICAL DEVICE

2.1 Description

The LIASON® MeMed BV® is an innovative immunodiagnostic solution to differentiate bacterial from viral infection. The assay measures and integrates the serum levels of circulating host-response protein signatures: TRAIL (tumor necrosis factor-related apoptosis inducing-ligand), IP-10 (interferon gamma-induced protein 10) and CRP (C-reactive protein). The result is a qualitative score – in less than an hour – discriminating between the bacterial and viral etiology of an infection.

3. STUDY OBJECTIVES AND DESIGN

3.1 Overall Study Design

BAST-ICU is a Pivotal study, observer-blind, randomized controlled clinical trial designed to evaluate the effect of implementing a BV-supported antibiotic treatment decision matrix on antibiotic use and clinical outcomes, comparing the treatment decision matrix (intervention) plus standard of care to standard of care alone (control) in an ICU population.

This RCT will be used to determine the effect of implementing a BV-supported antibiotic treatment decision matrix on antibiotic use (efficacy) *and* on a combined clinical endpoint among study participants (safety).

3.2 Objectives

3.2.1 Primary Objective(s)

To evaluate the combined endpoint of efficacy and safety at 28 days (approximately 4 weeks). This will include:

- Efficacy: Assessed by the use of antibiotics.
- Safety: Assessed by clinical outcomes.

3.2.2 Secondary Objective(s)

The assessment at 28 days will determine the overall effectiveness and safety of the intervention. To evaluate the following parameters:

- Antibiotic-free Days in ICU: The number of days patients remain in the ICU without antibiotic treatment.
- Use of Reserve/Restricted Antibiotics: The frequency and duration of the use of reserve or restricted antibiotics.
- Adherence to Recommendations: The degree of adherence to the recommended treatment guidelines and protocols.
- Incidence of Clinically Significant (Grade IV) Adverse Events: The occurrence of severe adverse events classified as Grade IV.
- Recurrent Infections: The rate of infection recurrence during the study period.
- Infectious Complications: The incidence of complications arising from infections.
- Length of Stay in ICU: The duration of the patient's stay in the intensive care unit.
- Death: The mortality rate during the study period.
- Colonization with Multi-Drug-Resistant Organisms: The incidence of colonization by multi-drug-resistant organisms.

3.2.3 Exploratory Objectives(s)

- To assess the incidence of colonization or infection with drug-resistant organisms.
- To assess the degree to which age, sex, gender, ethnicity may affect antibiotic prescription, appropriateness, and adherence to treatment recommendation (physician prescription behavior)

4. SELECTION AND ENROLLMENT OF PARTICIPANTS

Study Procedures will occur in the ICU from both MGH and RVH sites, with the RVH site serving as the coordinating center.

4.1 Number of Participants

Our target recruitment goal is 600 participants per group (1200 total participants) at participating MUHC sites.

During the pilot phase of the study, it was documented that the study population in ICU are often incapable of providing informed consent for themselves due to their health condition or due to the fact they are intubated. As of 17-Jun-2025, 40% of otherwise eligible patients could not be approached by the research team as they suddenly lost their capacity to consent for themselves. Without the possibility to approach the Legally Authorized Representative who makes health decisions on behalf of the patient, there is a significant risk the BAST-ICU trial may not meet its enrollment target therefore study objectives.

As this study represents minimal risks to participants, that medical decision-making remains in the treating team's hands, and the objectives of the study would not be met if only patients with capacity to consent are approached, the inclusion criteria are updated to include:

- Participant who have suddenly lost capacity to consent due to their health condition (intensive care) and for whom a Legally Authorized Representative can be approached and provide consent for the patient. The research team will seek the participant's consent (confirmation of consent or withdrawal) as soon as the participant regains capacity to consent.

4.2 Inclusion Criteria

All participants must meet ALL of the following inclusion criteria:

- i. Adults (≥ 18 years) at the time of consent;
- ii. Admitted to the Intensive Care Unit (ICU);
- iii. Started on antibiotics for any suspected or confirmed infection in the preceding 72 hours (about 3 days);
- iv. Treating doctor(s) willing to consider BV test result in antibiotic treatment decision making.
- v. Being able to provide informed consent. In case of sudden lost of capacity to consent due to the health condition (requires Intensive care), a Legally Authorized Representative will be approached by the study team.

4.3 Exclusion Criteria

Potential participants who meet ANY of the following criteria will be excluded:

- i. Severe immunocompromise/immunosuppression
 - a. Congenital immunodeficiency
 - b. HIV with $CD4 < 200$
 - c. Active chemotherapy and profound neutropenia ($ANC < 100$) expected to last > 7 days;

- d. solid organ or stem cell transplant within preceding 6 months AND active GVHD
- e. Receiving high dose steroids (Pred > 20mg/day for > or = 2 weeks)
- ii. Advanced metastatic cancer irrespective of treatment
- iii. Palliative intent, death imminent and inevitable within 4 weeks
- iv. Antibiotic to be discontinued within 24h (ex. Prophylaxis)
- v. Active infection diagnosed and treated with antibiotics within preceding 2 weeks
- vi. Previously included during the same hospitalization

4.4 Strategies for Recruitment

Participants will be recruited from two ICU clinic sites (MUHC: MGH and RVH). The ICU treating team will identify potential participants and will inform them about the research project. If they are interested, treating teams will ask the patient for authorization to be approached by the research team. If the potential participants are interested, study coordinator will present the study, and the consent process can begin.

Consent process:

A delegated research staff will read the ICF in its entirety with the participant and explain the study protocol. Time and opportunity to discuss with the treating team and relatives will be given, and all questions will be answered. After reflection, if the participant agrees to participate in the study, the ICF will be signed by the participant and the person obtaining the consent. A copy of the signed ICF will be given to the participant for their own records. The ICF will also be scanned and placed in their hospital medical chart.

E-consent:

1) The consent process for e-consent is the same as for wet-ink signature. REDCap, a secure FDA part 11 compliant platform, is used to collect signatures from the participant and the person obtaining consent and for participant's research file storage during the study. If the participant opts for electronic signature, they will receive a link by email which will lead them to the REB approved ICF in pdf format uploaded to REDCAP (there is no need to submit a e-consent form as the same consent is used).

4.5 Enrollment Procedures

Upon confirmation of eligibility and consent (Appendix I), each participant will be randomly allocated a randomization number and a unique Participant Identification (ID) number which will serve as their identifier throughout the study. Once a randomization number and Participant ID number have been assigned, they cannot be re-assigned to any other participant. This measure ensures that each participant's data remains distinct and accurately attributed. A participant cannot receive more than one ID number, ensuring that each participant's contributions to the study are accounted for singularly and accurately.

All participants will be given a participant identification card identifying them as participants in a research study. The card will contain study site contact information

(including direct telephone numbers) to be used in the event of an emergency. The investigator or qualified designee will provide the participant with a participant identification card immediately after the participant provides documented informed consent.

4.6 Co-enrollment Guidelines

Patients can be enrolled in other clinical trials if there is no conflict with the inclusion or exclusion criteria of the BAST-ICU study, and the other protocol is not in conflict with the means of data collection and publication of this protocol.

4.7 Pregnancy and/or breastfeeding

Pregnant or breastfeeding women can be included in this study if they meet the eligibility criteria. Since the study intervention is providing advice on antibiotic therapy that has already been prescribed by the treating team, there is no contraindication to exclude pregnant or breastfeeding women. As per standard of care, the pregnancy and breastfeeding status of potential participant will be reviewed and documented by the treating team.

5. PILOT Testing of Enrollment Processes and BV Score Validation

Before the implementation of the main study, a pilot phase will be conducted to refine the study enrollment procedures and validate the BV Score. Participants will be screened and enrolled but will not be randomized for the intervention, and their test results will not be used for decision-making.

5.1 Number of Pilot Participants

A total of 40 pilot participants will be included. Target population:

- Non-infected post-op patients (eg. post-cardiac surgery with no clinical, radiological or microbiological evidence of infection) (n= 10)
- Non-infected and non post-op patients (eg. CHF, trauma) (n=10)
- Patients with confirmed bacterial infection (eg. confirmed ventilator-associated pneumonia, bacteremia) (n = 10)
- Patients with presumed or confirmed viral pneumonia (without a confirmed bacterial superinfection) (n = 10)

5.2 Pilot Participant Eligibility Criteria

Study team members will screen eligible participants that are 18 years old belonging to any of the target populations.

5.3 Pilot Procedures

For each of the participants, a blood sample for BV testing will be collected on the day of enrolment and brought to the research laboratory for testing.

5.4 Pilot Data Collection and Analysis

Study team members (PI/Co-I and Pharmacist) will assess clinical and laboratory parameters and establish a consensus-based determination of bacterial/no-bacterial infection independent of BV results. Subsequently, BV results will be plotted on a receiver operating characteristic (ROC) curve to verify the cut-off values established by the manufacturer (BV <35: low likelihood of bacterial infection; 35 ≤65: equivocal; >65: high likelihood of bacterial infection) in this population.

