Optimization of AMU is dependent on accurate decision-making when appropriate diagnostic tests are obtained at the onset of infection. Although microbiologic tests (culture or nucleic acid-based amplification tests) are helpful to detect specific pathogens, they are not sufficient to lead to significant reductions in AMU or changes in clinical outcomes for hospitalized patients^{27,28}. Further, positive bacterial results can result from colonization or contamination and are not always indicative of infection, in fact can lead to over-treatment^{10,29,30,31–33}. Host response-based diagnostics tests could more accurately discriminate between non-infectious etiologies vs. microbial colonization vs. infectious disease, in an objective and quantifiable format³⁴. Procalcitonin (PCT) is the best studied of such markers, with several trials showing that test results folded into antibiotic decision support guidelines curb the use of antibiotics in some infectious syndromes with no apparent harm^{35–38} but other studies have demonstrated that a strategy of PCT combined with graded treatment recommendations provided no added value beyond usual care, despite the careful use of quality-improvement principles in the deployment of the intervention⁴².

MeMed BV® (referred to as BV) is a novel diagnostic assay that exploits a targeted, multiplexed host protein signature to distinguish between bacterial and non-bacterial infection, or no infection (e.g. colonization)⁴⁷. The selection of the proteins was based on extensive bioinformatic screening followed by computational models to identify the combination with the best discriminatory power. The score performs robustly across different patient subgroups (age, gender, comorbidities, time from onset of symptoms, pathogen species), and is superior to individual or combinations of known biomarkers in differentiating between bacterial vs non-bacterial infections^{48–50}. Its diagnostic accuracy has now been validated in >20,000 patients presenting with respiratory infections or fever without a source in emergency and inpatient wards in different countries, with BV score >65 predicting bacterial infection with a sensitivity of 98%, and BV<35 having a negative predictive value of 98.8%^{51–53}. The test is now Health Canada-approved, but whether it can be used to support antibiotic treatment decisions in ICU populations is not yet known as critically ill patients were excluded from previous studies.

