8.9 Antibiotic treatment decision procedure specific to the control group

For the control group, the BV test result will remain masked to investigators and treating team members.

The antimicrobial stewardship study team (Pharmacist and PI/Co-I) will issue antibiotic treatment suggestions following the standard decision matrix outlined below. The recommendation will be shared with the treating team.

Necessity of antibiotics	Recommendation on antibiotic treatment
Clearly not indicated	STOP (strong recommendation)
Somewhat indicated	Stop (moderate recommendation) or continue --> review choice*
Indicated (Justified)	Continue antibiotic --> review choice *
Cannot be rated	Consider expert (ID) consultation

For all cases where necessity of antibiotics was rated as “somewhat indicated” or “indicated”, the choice of antibiotics will be rated. The final recommendation (to stop, continue or change antibiotic) is shared with the treating team.

Choice of antibiotic	Recommendation on antibiotic treatment
Far too broad	Change drug (strong recommendation)
Somewhat too broad	Consider changing drug (moderate recommendation)
Appropriate choice	Continue same drug
Somewhat too narrow	Change drug
Cannot be rated	Consider expert consultation (ID)

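### Ten confirmed bacterial cases cannot verify the BV cut-offs in ICU: even a perfect pilot would not rule out missing one bacterial infection in five

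*Protocol*

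**What the plan says.** Section 1.1 cites a sensitivity of 98% for BV above 65 and a negative predictive value of 98.8% for BV below 35. It adds that use in ICU is untested because "critically ill patients were excluded from previous studies". The pilot is the ICU check planned before the main trial. The synopsis describes its design as validation of the BV Score, with an objective covering both feasibility and BV performance. Section 5.4 states the analysis: "BV results will be plotted on a receiver operating characteristic (ROC) curve to verify the cut-off values established by the manufacturer", against a consensus diagnosis made independently of BV.

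Section 5.1 fixes the size: "A total of 40 pilot participants will be included", in four groups of 10. The one bacterial group is "Patients with confirmed bacterial infection (eg. confirmed ventilator-associated pneumonia, bacteremia) (n = 10". Two of the three comparator groups are non-infected. The third is "Patients with presumed or confirmed viral pneumonia (without a confirmed bacterial superinfection) (n = 10". The protocol gives no target accuracy, precision or acceptance rule for the pilot.

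The main trial enrols patients started on antibiotics for a suspected or a confirmed infection (section 4.2). BV is measured in every participant (section 9.3). In controls "the BV test result will remain masked to investigators and treating team members" (section 8.9). BV values are kept in the final dataset (section 16), but no objective in section 3.2 concerns diagnostic accuracy.

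**The concern.** To verify a cut-off is to conclude that the test performs acceptably there. The main risk in this trial is a bacterial infection with a BV score below 35. In the matrix of section 8.10 that score leads to a strong stop recommendation when necessity is rated as somewhat indicated or cannot be rated. How often this happens is a question of sensitivity, and in the pilot only the 10 bacterial cases inform it.

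The mix of cases matters as well. The bacterial group contains no suspected but unconfirmed infections, although such patients are eligible for the trial and are where the BV result has most influence on the recommendation.

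At stake is what may be claimed before and after the trial. If the pilot is reported as having verified the cut-offs, a null or harmful main result is likely to be read as a failure of the matrix when poor accuracy of the test in ICU remains a live explanation. Section 1.3 lists how such results would be explored: low antibiotic use in controls, particular adverse events, subgroups. Test accuracy is not on the list.

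**Working it through.** **Inputs.** Bacterial cases n = 10 and non-bacterial cases 30 (section 5.1; 10 + 10 + 10 + 10 = 40, as stated). Reference sensitivity 98% (section 1.1, given for the cut-off of 65; at 35 it could only be the same or higher). Controls: 600 (section 4.1). The 20% miss rate is an assumption used for illustration, since the protocol sets no tolerable rate. A miss is a bacterial case on the wrong side of the cut-off in question. The pilot size has no stated statistical basis, so there is no figure to reproduce.

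**1. What the best result would show.** With 10/10 correct, the exact (Clopper-Pearson) two-sided 95% lower limit is 0.025^(1/10) = 0.692. The one-sided 95% limit is 0.05^(1/10) = 0.741. A perfect pilot is thus compatible with missing 26% to 31% of bacterial infections. With 9/10 the exact 95% interval is 55.5% to 99.7%.

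**2. How often a poor cut-off would show itself.** For true sensitivity 80%:
- P(no miss) = 0.8^10 = 0.107
- P(at least one miss) = 1 − 0.107 = 0.893
- P(at least two) = 1 − 0.107 − 10 × 0.2 × 0.8^9 = 0.624

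For true sensitivity 98%:
- P(at least one miss) = 1 − 0.98^10 = 0.183
- P(at least two) = 0.016

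| Rule for raising a flag | Flag if sensitivity is 80% | False flag if sensitivity is 98% |
|---|---|---|
| Any miss | 89% | 18% |
| Two or more misses | 62% | 1.6% |

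Seen from the other side, accepting the cut-off only after 10/10 wrongly accepts an 80% sensitivity with probability 10.7%. No rule with n = 10 keeps that error at 5%.

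**3. What would be needed.** With zero misses, excluding a 20% miss rate takes n ≥ ln(0.05)/ln(0.8), which is 14 cases (one-sided 95%), or ln(0.025)/ln(0.8), which is 17 (two-sided). An exact test showing sensitivity above 80% with at least 80% power needs 22 cases (one-sided 0.05) or 26 (one-sided 0.025) if the truth is 98%, and 30 or 41 if it is 95%.

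**4. Specificity.** 30/30 correct gives an exact 95% lower limit of 0.025^(1/30) = 0.884, so the comparators are less limiting in number. But 20 of the 30 are known to be non-infected.

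**5. What the control arm could add.** The documents do not give the proportion of participants with bacterial infection. Assuming 30% to 70%, 600 controls contain 180 to 420 cases. For a sensitivity of 90%, the half-width 1.96 × √(0.9 × 0.1/n) is 4.4 points at n = 180 and 2.9 points at n = 420. An observed 98% would have an exact 95% interval of 94.4% to 99.4% (n = 180) or 96.3% to 99.2% (n = 420). These widths take the reference diagnosis as error-free.

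**The case against.** The strongest reply is that this is mainly wording. The pilot also has a feasibility aim, its results guide no treatment, and section 4.1 already reports pilot experience to June 2025, so its size may no longer be open to change. The study recommendations are not binding (section 10.1), and a BV score below 35 with antibiotics rated as justified goes to expert consultation (section 8.10). All of this stands. It limits the risk to patients, but it does not make verification a conclusion that 10 cases can carry.

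Four stronger readings are tempting and not supported:
- **The pilot could not detect a one-in-five miss rate.** At 80% sensitivity at least one miss would appear with probability 89% if the cases are representative. The supportable statement is that the pilot cannot rule such a rate out or reliably tell it from good performance.
- **The cut-offs drive every recommendation in the BV arm.** In section 8.10 the stop recommendation for antibiotics clearly not indicated is the same on both sides of 35. The continue recommendation for justified antibiotics is the same on both sides of 65. Choice of drug is rated without BV.
- **A failing test could not be told from poor adherence.** Adherence is a secondary objective (section 3.2.2), reasons for not following a stop recommendation are recorded (section 14.5), and a per-protocol analysis is planned (section 12.7).
- **Leaving the control-arm BV values without an accuracy analysis is an error.** Masking is required by the design, the values are kept, and an analysis plan not shown here may use them. It is a missed opportunity in the protocol.

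**Conclusion.** The claim to validate the score and verify its cut-offs in ICU is not supportable from this pilot. With 10 bacterial cases the best possible result leaves a 95% lower limit of 69% for sensitivity, and a single miss widens the interval to 55.5% to 99.7%. A flag at two misses has about 62% power to pick up 80% sensitivity; a flag at any miss has 89% power with an 18% false-alarm rate at 98% sensitivity.

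The interval limits rest only on n = 10. The detection probabilities rest on the assumed 80% and on the 10 cases representing the trial's infections. Clear-cut confirmed cases would probably make misses less likely to appear, by an amount the documents do not allow one to calculate. The easy-case argument is only partial on the comparator side, where presumed viral pneumonia is allowed.

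The point does not touch the primary endpoint, the sample size or the randomization. It concerns what may be said about the test, and how the trial's result can be explained.

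**What to change.** **Pilot wording.** In the synopsis and section 5, describe the pilot as a feasibility study with exploratory BV data, and replace the statements that it validates the score or verifies the cut-offs. In section 5.4, report sensitivity and specificity at 35 and at 65 with exact 95% confidence intervals beside the ROC curve. Predictive values from the pilot should not be carried over, because its bacterial share is fixed by design at 10 of 40. This costs only text.

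**Control-arm accuracy analysis.** In section 12, pre-specify a secondary analysis in the control arm, where BV is masked and cannot have influenced treatment. Compare BV at 35 and 65 with a bacterial/non-bacterial judgment made by the study team without knowledge of BV, as in section 5.4, with 95% confidence intervals and by necessity rating.

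The cost is one added chart judgment for each of about 600 controls, because the form in section 8.8 rates diagnostics, necessity and choice of antibiotic but not bacterial origin. The protocol should also say that error in this reference judgment and the unknown bacterial prevalence limit the precision. It should add that the analysis helps to interpret the trial's result and does not verify the cut-offs before the trial uses them.
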